### Data Analysis Plan

Recruitment data will be summarized, including the number of potential participants screened, number excluded for each inclusion/exclusion criteria, and number of eligible individuals agreeing to participate. To assess program reach, we will calculate proportion of subjects enrolled to total eligible subjects and compare enrollment rates by region (rural or urban) using the chi-square test. Baseline demographics will be summarized and compared between study groups using the chi-square test for categorical variables and the two-sample t-test/rank sum test for continuous variables. Percentage of enrolled participants completing each follow-up assessment (i.e., study retention) and ratings of treatment acceptability will be compared between study groups using the chi-square test (Fisher's exact test). Facebook use and engagement will be summarized using descriptive statistics and time effects over the 3 month treatment period will be assessed via mixed effects models as appropriate to explore sex, age group, and region effects respectively. The association of COS baseline scores and Facebook engagement will be evaluated using linear regression. Qualitative (content) analysis will be utilized to generate themes in Facebook postings and comments.

Biochemically-confirmed 7-day point prevalence tobacco use rate at 1, 3, and 6 months follow-up will be compared between conditions using logistic regression (with odds ratio and 95% confidence interval estimates). Using an intent-to-treat approach, we will classify as smoking participants eligible but lost to follow-up or not providing biochemical verification of smoking abstinence. We will also explore multiple imputation methods to classify lost to follow-up as cigarette smokers or non-smokers and conduct sensitivity analyses as appropriate. For these analyses, we will adjust for stratification factors (sex, age group, urban/rural region) and any baseline differences observed between treatment conditions if data allow (i.e., adequate numbers of subjects verified as abstinent). Secondary analyses using logistic regression will explore intervention effects on self-reported abstinence from all tobacco/nicotine products, quit attempts, and self-reported tobacco treatment utilization. We will follow procedures suggested by MacKinnon to assess mediation, fitting logistic/linear regression models to the data.

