**Specific Aim 2 (phase 4):** To conduct a randomized pilot trial to evaluate feasibility, uptake, consumer response, and potential efficacy of the Facebook intervention compared with a control condition. In the pilot trial, 60 adult AN people who smoke will be randomized to the Facebook intervention or to a

control condition (quitline/treatment referral). Assessments will occur at baseline, 1, 3 and 6 months follow-up.

Our sub-aims are to:

- a. Examine feasibility of delivering an intervention through social media as determined by recruitment and retention rates, treatment acceptability ratings, and Facebook intervention exposure and engagement.
- b. Estimate potential magnitude of the intervention effect compared to the control condition on biochemically verified, 7-day point prevalence smoking abstinence rate at 1, 3, and 6 months follow-up.
- c. Explore intervention effects on secondary outcomes: self-reported abstinence from any tobacco or nicotine product, quit attempts, and use of the state quitline or any evidence-based smoking cessation treatment (pharmacological or behavioral) through 6 months follow-up.
- d. Explore sex, age, and region (urban/rural) effects on Facebook exposure and engagement, smoking abstinence, smoking treatment utilization, and quit attempts.
- e. Explore interdependence (relationship orientation and collaborative efforts in decision making and lifestyle changes) as a culturally relevant mediator of intervention efficacy.
- f. Since the pilot testing period took place over the COVID-19 pandemic, we will explore the self-reported impact of COVID-19 perceived risks, severity, and COVID-19-related anxiety, stress, financial impacts, social isolation, and social support on our primary outcome of smoking treatment utilization and cessation at 6-months follow-up.
- g. Adapt the intervention and procedures in preparation for a future large-scale efficacy randomized trial.

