Data from the Facebook application programming interface will be extracted using Sprinklr software. For each week of the study, we will extract for each intervention participant the following engagement metrics: # of logins; # digital story downloads; # user-generated posts, comments, questions and responses to the moderator or other users; # likes, shares and reactions; and time and date of each. In addition, a transcript of all participant postings will be generated for content analysis.

Smoking abstinence. At each follow-up, we will obtain the participant's self-reported cigarette use in the past 7 and 30 days, number of cigarettes smoked per day, and quit attempts. We will also assess current use of ST/*iqmik*, e-cigarettes, and other tobacco/nicotine products. All participants will be mailed a saliva kit with a collection tube and postage paid return envelope. Participants returning a saliva specimen will receive an additional \$25 Visa gift card. The specimen will be shipped to and assayed by Mayo Clinic laboratories. This approach has been feasible in several NIH-funded clinical trials conducted in AK (DA 025156; CA164533; CA153605) and in other studies; and biochemical verification is recommended in randomized trials with sample sizes under 500. Point prevalence smoking abstinence will be defined as no smoking (not even a puff) for the last 7 days verified with salivary cotinine level <15 ng/ml. Use of nicotine replacement therapy and ST/*iqmik* use will be assessed at follow-up because its use would elevate cotinine concentrations. If participants indicate use of e-cigarettes, saliva cotinine and reported e-cigarette use will be recorded and analyzed separately from biochemically verified cigarette smoking abstinence.

Smoking Treatment Utilization. As a secondary aim, we will document self-reported use of any evidence-based cessation aid during the 6 month study period. For this pilot study, it is not practical to objectively verify self-reported treatment use given heterogeneity of potential services/medications used.

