Biochemically- confirmed 7-day point prevalence tobacco use rate at 1-, 3-, and 6-months follow-up will be compared between conditions using logistic regression (with odds ratio and 95% confidence interval estimates). Using an intent-to-treat approach, we will classify as smoking participants eligible but lost to follow-up or not providing biochemical verification of smoking abstinence. We will also explore multiple imputation methods to classify lost to follow-up as cigarette smokers or non-smokers and conduct sensitivity analyses as appropriate. For these analyses, we will adjust for stratification factors (sex, age group, urban/rural region) and any baseline differences observed between treatment conditions if data allow (i.e., adequate numbers of subjects verified as abstinent). Secondary analyses using logistic regression will explore intervention effects on self-reported abstinence from all tobacco/nicotine products, quit attempts, and self-reported tobacco treatment utilization. We will follow procedures suggested by MacKinnon to assess mediation, fitting logistic/linear regression models to the data.

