### Endpoints

**Primary:** The primary outcomes will be feasibility (e.g., Facebook engagement) and the biochemically- verified smoking abstinence rate at 1, 3, and 6 months follow-up.

**Secondary:** Secondary outcomes will include self-reported smoking cessation treatment utilization and

abstinence from all tobacco/nicotine products. We will also explore interdependence (relationship orientation and collaborative efforts in lifestyle change) as a culturally relevant mediator of intervention efficacy.

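### The secondary outcome of abstinence from all tobacco and nicotine products is scored on self-report alone, although the trial seeks cotinine from everyone; a cotinine-verified version should be reported beside it

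*Combined protocol and SAP*

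**What the plan says.** **Secondary outcome.** Sub-aim c of Specific Aim 2 names it as "self-reported abstinence from any tobacco or nicotine product". The Data Analysis Plan under Phase 4 says "Secondary analyses using logistic regression will explore intervention effects on self-reported abstinence from all tobacco/nicotine products". The second copy of that plan, under Data Analysis, lists "self-reported abstinence from all tobacco/nicotine products, quit attempts, and self-reported tobacco treatment utilization". The Endpoints section lists "abstinence from all tobacco/nicotine products" with no verification step.

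**Primary abstinence outcome.** The Measures section (Smoking abstinence) defines it as "no smoking (not even a puff) for the last 7 days verified with salivary cotinine level <15 ng/ml". For participants without follow-up or without verification, the Data Analysis Plan says "we will classify as smoking participants eligible but lost to follow-up or not providing biochemical verification of smoking abstinence".

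**The assay.** Measures says "All participants will be mailed a saliva kit with a collection tube and postage paid return envelope". Table 3 schedules saliva cotinine at 1, 3 and 6 months, and gives verification of smoking abstinence as its purpose. Measures also notes that "biochemical verification is recommended in randomized trials with sample sizes under 500"; this trial has 60 participants. The same section says that NRT and smokeless tobacco or iqmik raise cotinine.

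Nowhere is the cotinine result, or the rule that unverified counts as smoking, applied to the all-product outcome.

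**The concern.** Someone abstinent from every product is necessarily abstinent from cigarettes, so all-product abstinence is the stricter state. Yet it has the looser scoring: the cigarette outcome needs a confirming assay and the all-product outcome does not. A returned specimen that contradicts the participant's answer changes the primary classification and leaves the secondary one untouched.

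Participants cannot be unaware of their condition. One arm spends 3 months in a moderated Facebook group and the other receives referral only (Table 2). The section on content for moderator postings says the messages focus on giving up all tobacco and nicotine products. Social pressure to report abstinence may therefore be stronger in one arm, on exactly this outcome. The exploratory estimate could then be shifted by reporting behavior, in a way the trial already has data to detect.

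**Working it through.** The plan gives no figure to reproduce here: 30 per arm is stated without abstinence rates, misreporting rates or saliva return rates. The check therefore compares scoring rules, followed by illustrations on assumed inputs.

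**1. Scoring participants who deny every product and NRT**

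| Saliva result | Primary (cigarettes) | Secondary (all products) | Reading |
|---|---|---|---|
| Cotinine <15 ng/ml | Abstinent | Abstinent | Agree |
| Cotinine ≥15 ng/ml | Smoking | Abstinent | Secondary contradicted by the assay |
| Not returned | Smoking, by convention | Abstinent | Different conventions, no contradicting datum |

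Only the second row is a conflict with observed data.

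**2. Is a reason given for leaving this outcome unverified?** Measures explains self-report for treatment use, where the variety of services and medications makes checking impractical. That reason does not carry over to product use, because the specimen is already requested. Cotinine also fits this outcome well. Smokeless tobacco, which complicates verification of cigarette abstinence, is a true failure for all-product abstinence. NRT is the source that needs its own rule.

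**3. How many participants might be involved?** Assume 6 of 30 in an arm deny all products and NRT, 60% to 90% return saliva, and 0% to 25% of returned samples are at or above 15 ng/ml.
- Contradicted by assay = 6 × return × share ≥15. This runs from 0 to 6 × 0.90 × 0.25 = 1.35 people.
- Not returned = 6 × (1 − return). This runs from 6 × 0.10 = 0.6 to 6 × 0.40 = 2.4 people.
- All who are abstinent in the secondary but smoking in the primary: from 0.6 (90% return, 0% high) to 2.4 + 6 × 0.60 × 0.25 = 2.4 + 0.9 = 3.3 people.

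**4. What could differential misreporting do?** Let p be true abstinence and m the share of non-abstinent participants who claim abstinence. Observed abstinence = p + (1 − p)m. All values are assumed.

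| True rates (Facebook, control) | m (Facebook, control) | Observed rates | Odds ratio | True odds ratio |
|---|---|---|---|---|
| 10%, 10% | equal in both arms | equal | 1.0 | 1.0 |
| 10%, 10% | 10%, 5% | 19.0%, 14.5% | 1.38 | 1.0 |
| 10%, 10% | 15%, 5% | 23.5%, 14.5% | 1.81 | 1.0 |
| 10%, 10% | 20%, 5% | 28.0%, 14.5% | 2.29 | 1.0 |
| 20%, 10% | 10%, 10% | 28.0%, 19.0% | 1.66 | 2.25 |

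For example, in the fourth row 0.10 + 0.90 × 0.20 = 0.280 and 0.10 + 0.90 × 0.05 = 0.145, so the odds ratio is (0.280/0.720)/(0.145/0.855) = 2.29. In the last row, equal over-reporting pulls the rate ratio from 2.0 to 0.28/0.19 = 1.47.

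**5. Set against sampling error.** With 30 per arm, the expected counts in the fourth row are 8.4 and 4.35. The standard error of the log odds ratio is √(1/8.4 + 1/21.6 + 1/4.35 + 1/25.65) = 0.66. The approximate 95% interval around 2.29 is 0.63 to 8.3.

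**The case against.** The strongest reply is that this is a declared choice. The outcome is labelled self-reported wherever its analysis is described, it is only to be explored, and the Design Overview omits it from its list of secondary endpoints. Verified and self-reported abstinence are expected to differ and can both be reported. This stands, and is why the self-reported outcome should be kept.

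Several stronger readings are tempting, and the documents do not support them.
- **That the Stage II decision is compromised.** Sample Size Calculation, and its counterpart in the Data Safety Monitoring Plan, tie the decision to a doubled abstinence rate at 6 months and to odds ratios for smoking abstinence. Nothing uses the all-product outcome for sizing or for proceeding.
- **That an unreturned specimen is a contradiction.** Scoring it as smoking is a conservative convention, not an observation. The plan itself adds multiple imputation and sensitivity analyses for participants lost to follow-up.
- **That the verified version should replace the self-reported one.** That would demote the one abstinence estimate that does not depend on mailed-back saliva. The verified version would also overlap heavily with the primary. With the same cotinine cut-off and missing-data rule, the two would separate mainly for people who report another product yet test below 15 ng/ml.
- **That a spurious effect is to be expected.** Every over-reporting rate above is assumed, the null distortions require a two- to four-fold difference between arms, and the interval in step 5 is wide.

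NRT is also a real difficulty. The plan does not say whether it counts as a nicotine product, and the quitline promoted to both arms can supply it. Dropping NRT users would be a post-randomization exclusion.

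None of this removes the central case: a denial of all products with a specimen at or above 15 ng/ml is scored as abstinence.

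**Conclusion.** The point holds in a limited form. An exploratory secondary outcome disregards an assay sought from every participant at each follow-up. It can therefore count as abstinent someone whose own specimen says otherwise, and because participants know their condition, the frequency of this could differ by arm. The primary analysis and the 6-month doubling criterion are untouched.

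The size is unknown. The documents give no misreporting or return rates, so the counts of 0 to 1.35 contradicted participants per arm (if 6 of 30 claim abstinence) and the odds ratios of 1.38 to 2.29 are illustrations only. The recommendation rests on the plan's own preference for verification in trials of this size and on the low cost of using a result already collected.

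**What to change.** In both copies of the Data Analysis Plan:
- Keep the self-reported all-product outcome as declared.
- Add a cotinine-verified version beside it at each follow-up: report of no tobacco or nicotine product, plus salivary cotinine <15 ng/ml at that visit. Count a missing survey or specimen as not abstinent, as for the primary.
- State in advance whether NRT counts as a nicotine product and how NRT users are scored. Keep all randomized participants in the denominator.
- Report by arm the cross-tabulation of self-reported all-product abstinence against cotinine (<15 ng/ml, ≥15 ng/ml, not returned).

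The cost is SAP wording and one extra derived variable, with no new specimen or assay. The downsides are that fewer people count as abstinent in the verified version, some true abstainers who do not return saliva are scored as failures (as the primary already accepts), and the verified outcome adds limited information beyond the primary. The cross-tabulation also gives Stage II a first look at misreporting by arm.

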### **Study Dissemination Activities**

After receiving Tribal review and approval, findings relevant to the community will be disseminated through presentations at regional and national community events and postings on websites and newsletters. Findings relevant for the scientific community will be presented at conferences and published in peer-reviewed journals. All manuscripts for publication and all abstracts for presentations will be submitted to ANTHC for Tribal review and approval prior to submission to a journal or other public venue.

Additionally, after receiving tribal review and approval of the following, findings relevant to the Alaska Native communities have been developed into a newsletter. In phases 3 and 4, as part of the consent process, we asked participants permission for re-contact after the study ended. We will send the newsletter only to those who provided consent for future contact in phases 3 and 4. In phases 1 and 2, we did not ask participants for permission to contact them in the future. Because sharing results is an important part in the research process, we will send the newsletter to phase 1 and 2 participants only with AIRB approval. The newsletter only shares the results of the CAN Quit study, and does not invite people to participate in future research.

Should any 'return to sender' letters occur, we will simply recycle these letters.

**Project Timeline (Table 4)**

Table 4: Timeline												
Tasks	Year 1				Year 2				Year 3			
Month:	3	6	9	12	15	18	21	24	27	30	33	36
IRB/tribal approvals	X											
Phase 1-3												
Pre-testing		X	X	X								
Develop/beta test prototype					X	X	X					
Phase 4												
Pilot trial recruit/intervention							X	X	X			
Follow-up								X	X	X	X	
Analysis										X	X	
Dissemination												X

**Resources:** Describe the available resources to conduct the research (personnel, time, facilities, mentor commitment, etc.):

various tribal health regions in AK; with experience using social media and some being former smokers. Quarterly phone or in-person meetings with CAB members will guide all study activities. Members will receive an honorarium and a meal will be provided for in-person meetings.

### **General Approach: Stage Model of Behavioral Therapies Development Research**

Our approach follows the three-stage model of behavioral therapies development and the proposed aims correspond to the two sub-stages characterizing Stage I work. In Stage Ia formative work, we will develop the Facebook intervention. In Stage Ib, we will use rigorous design and methodology to evaluate the intervention's feasibility and potential efficacy. Stage Ib results will inform a future R01, Stage II, randomized efficacy trial

A 3 year timeline is proposed. The formative work will take place in months 1-20 and recruitment for the pilot trial will occur in months 21-27, with intervention, follow-up and analyses completed by month 33. The remaining months will be spent on dissemination activities.

The study will be conducted at the ANTHC in Anchorage and at Mayo Clinic. All data collection and the intervention will be conducted by study staff at ANTHC and Mayo Clinic. Data will be collected and maintained by the Mayo Clinic Survey Research Center via Qualtrics software. Mayo Clinic will collect and maintain data electronically in a secure REDCap database.

Mayo Clinic study staff will be engaged in research activity at a non Mayo Clinic site. *Description of the activity that will be conducted by Mayo Clinic study staff.*

The study will be conducted at the ANTHC in Anchorage and at Mayo Clinic. All data collection and the intervention will be conducted by study staff at ANTHC and Mayo Clinic. Several procedures are established to monitor the quality assurance of the study. For qualitative data collection, a semi-structured interviewer guide will be developed and the Anchorage-based Project Coordinator will conduct the interviews. [name] and [name] will provide training for the project coordinator on-site in Anchorage including 4 hours of didactic instruction followed by 4 practice hours of mock interviews and a certified completion interview. All sessions will be audiotaped. These transcripts will be coded by [name] to assess counselor adherence to the proscribed intervention, and feedback will be provided during weekly research team teleconferences.

Mayo Clinic social media department will create the Facebook group page, develop the content library of moderator postings, and set up the software to capture participant use data. A random sample of 20% of moderator postings and responses to participant inquiries and discussions will be selected every week for the first four weeks and monthly thereafter. These transcripts will be coded by [name] to assess moderator adherence to the proscribed intervention, and feedback will be provided during weekly research team teleconferences.

A manual of study procedures will be developed for the project coordinator. [name], a Mayo Clinic research assistant and clinical trials coordinator, will travel with [name] to Anchorage, Alaska, to train the study staff on the data collection and other study procedures including monitoring of adverse events. We will use the same coordination, communication, and quality control procedures successfully utilized in our previous work. For ongoing trials in Alaska, we hold weekly conference calls with study staff in AK and at Mayo Clinic to discuss progress and problem solve issues related to recruitment and data collection. We also monitor quality control of the data on site through review of participant forms and procedures every 3 months. [name], Biostatistician on this protocol, will oversee the transfer of data forms, electronic data, and data storage. The Mayo Survey Research Center will electronically transfer all data to [name]. The quality of the data (data checks) including missing data and presence and frequency of outliers will be monitored once per month by [name]. For study recruitment, [name] will track posting of ads through FB and in Alaska local newsletters and websites. AK study staff will also recruit in person using flyers and different methods of in person recruitment.

All measures will be administered online using Qualtrics software, a data security service. An email

link will be sent automatically by the Mayo Clinic Survey Research Center to complete the assessment. If a participant does not complete online assessments, he/she will be contacted through email or by phone by the project coordinator and prompted to complete the assessment. Data collected from survey responses will be handled and maintained by the Mayo Clinic Survey Research Center and a de-identified database of responses will be provided to the investigators. Interview forms and audio tapes will be labeled with subject ID numbers only; all personal identifiers will be removed before the data are sent to Mayo Clinic for analysis. At Mayo Clinic the audio tapes will be stored in a locked file drawer accessible only to the PI, [name], Co- Investigator, [name], and the Research Assistant, [name]. These will be destroyed once the interviews are fully transcribed.

A trained research assistant at Mayo Clinic will mail the saliva sample kit to the participant; and the saliva samples, labeled with a subject ID number only, will be shipped directly back to Mayo Clinic for analysis of cotinine. Once the specimen sample is processed and results posted, the sample will be destroyed immediately.

The study staff in Anchorage and Rochester will monitor any reports or observations of medical problems or severe depression or other psychiatric symptoms in participants. Drs. [name] and [name], licensed clinical psychologists, will be consulted by telephone to consult with the study staff as needed.

